6.2. Treatment Groups

6.2.1. CHRONOS-A

- Arm 1 (Control arm): Radical therapy (prostatectomy or radiotherapy [external beam or brachytherapy]). The type of radical therapy will be determined by physician or patient preference.
 - o In radiotherapy patients, neoadjuvant ADT permitted and if given, minimum 3 months and maximum 6 months duration.
 - We anticipate lymph node treatment in this group is not required but for cause lymph node treatment will be permissible if strong clinical preference is demonstrated.
 - If an extended lymph node dissection is anticipated this will need to be discussed in a central review by the surgery subgroup.
 - As per Radiotherapy Trials Quality Assurance (RTTQA) centres and physicians delivering radiotherapy will need to be approved.
 - o Radiotherapy detailed protocols will be set out in a separate SOP.
 - Surgeons and surgical centres currently are approved as a national commissioning programme so any centre or surgeon permitted to carry out radical prostatectomy in standard NHS practice will be permitted to deliver prostatectomy within this trial.
 - Prostatectomy details will be set out in a separate SOP.
- Arm 2 (Intervention arm): Focal therapy alone (high intensity focused ultrasound [HIFU] or cryotherapy or other validated energy modality as per physician/patient decision/choice. Other energy modality will only be added after TSC and TMG approval and a substantial amendment approved by all required bodies.

- A second treatment either in-field or out-of-field will be permitted either after the MRI and control biopsy showing clinically significant cancer at 12-months or due to suspicion of residual or new contralateral disease at a future date with a positive biopsy for clinically significant cancer.
- Cryotherapy can be used after HIFU and HIFU can be used after cryotherapy. This second focal therapy session will be part of the focal therapy intervention
- o Focal therapy details will be set out in a separate SOP.

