6.2.2. CHRONOS-B

- Arm 1 (Control arm): Focal therapy alone (high intensity focused ultrasound [HIFU] or cryotherapy or other validated energy modality as per physician and centre choice). A second treatment in-field, or a first focal ablation to an out-of-field progressive or de novo lesion will be allowed but will be regarded as failure events for the purpose of CHRONOS-B. Cryotherapy can be used after HIFU and HIFU can be used after cryotherapy.
- Arm 2 (Intervention arm): Neoadjuvant finasteride 5mg once daily for a minimum of 12 weeks (84 days) followed by focal therapy (as per control arm).
- Arm 3 (Intervention arm): Neoadjuvant bicalutamide 50mg once daily therapy for 12 weeks (84 days) followed by focal therapy (as per control arm).

Other arms can be added in future, as part of the main trial, with protocol amendments.

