Biopsy				X (focal therapy arms)				
Treatment		X (these vary in length)						X (focal therapy arms – a second treatment will be permitted for a histologically confirmed recurrent, residual or new out-of-field disease)
Clinical assessment (optional, only if required)			Х	Х	х	х	Х	
PROMS questionnaires	Х		х	х		х		X (every 12 months, at 24, 36, 48 and 60 months visits)

Imperial Clinical Trials Unit	STATISTICAL ANALYSIS PLAN: FEASIBILITY	CHRONOS
----------------------------------	--	---------

[figure not shown]
Review/ reporting of patient AEs/SAEs		Х	Х	Х	Х	Х	Х	Х
Blood and urine tests including those for biobanking (optional)	Х		Х	Х				X

Time window for each visit will be +/- 4 weeks

Minimum length of follow up for the pilot will be 3 months from treatment for each patient. Then treatment will revert to standard of care.

[figure not shown]

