The reasons for ineligibility and withdrawal will be collected and recorded for CHRONOS-A and CHRONOS-B separately. Kaplan-Meier plots will be presented to show time from randomisation to withdrawal for CHRONOS-A and CHRONOS-B separately. Baseline characteristics will be compared between those who completed the Internal Pilot phase of the study, and those who withdrew from the Internal Pilot phase of the study.

Throughout the trial, adverse events will be recorded using the designed eCRFs. Reported adverse events (AEs) and serious adverse events (SAEs) will be listed, and then summarised, by treatment arm, in terms of severity grade (using v4.0 CTCAE grading) and causal relationship to treatment, for CHRONOS-A and B separately. Expected adverse events which are not to be reported as SAEs are listed in Appendix 1.

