9.8. Safety Analysis

Safety analysis will consist of tabulating the frequency of serious adverse events, and is part of the primary outcome analysis detailed in Section 9.3.

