10.4. Analysis of End Points

The following analyses will be conducted separately for each of the two patient populations defined in the table above (Section 10.3).

STATISTICAL ANALYSIS PLAN: FEASIBILITY

CHRONOS

The mean number of patients recruited and randomised per month, per centre (including only the months in which the centre is open and recruiting), will be calculated. Overall recruitment and randomisation rates will also be calculated, along with their corresponding 95% confidence intervals. Recruitment rate is calculated as the number of participants recruited out of the total number approached. Randomisation rate is calculated as the number of participants randomised out of the total number recruited. Graphs displaying the recruitment and randomisation rates over time will be presented. A graph displaying the actual vs target recruitment rates will also be presented. These analyses will be conducted for CHRONOS-A and CHRONOS-B.

Compliance will be summarised using summary statistics, by treatment arm, for the time between consecutive visits, from screening visit to final follow-up visit (Visit 3 for feasibility phase). The proportions of patients, in each treatment arm, with a missing or delayed visit will also be presented. A missed visit is a visit at which no information was collected. A delayed visit is a visit which is outside of the visit window defined in the Visit Schedule (Section 6.7.2). These statistics will be presented for CHRONOS-A and CHRONOS-B.

Summary statistics for time between consent and randomisation, and randomisation and treatment will be presented by treatment arm. Summary statistics will also be presented for time between consecutive visits, by treatment arm.

For CHRONOS-B only, summary statistics will also be presented for time between randomisation and start of neoadjuvant treatment, and time between start of neoadjuvant treatment and start of focal therapy.

Treatment, for CHRONOS-A and CHRONOS-B, is recorded at Visit 2 (Treatment Visit). For focal therapy arms (CHRONOS-A (Focal arm) and CHRONOS-B) treatment is recorded by date of treatment and completed treatment details at Visit 2. For the radical arm of CHRONOS-A, treatment is recorded by date of visit 2 and completed treatment details on Radiotherapy/Brachytherapy Log and Prostatectomy Log at Visit 2. The proportions of patients in each treatment arm who underwent treatment will be presented, along with their corresponding 95% confidence intervals.

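### Pilot adverse event tables give crude percentages by arm with no common observation window or time at risk, so arms with a long pre-treatment phase may be observed for longer

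*SAP*

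**What the plan says.** SAP 9.3 has adverse events recorded throughout the trial and then says "Reported adverse events (AEs) and serious adverse events (SAEs) will be listed, and then summarised, by treatment arm, in terms of severity grade", and also by causal relationship to treatment. Tables 2.18 and 2.19 give men with events (at the highest grade or relationship) and all events. Tables 2.21 and 2.22 do the same for serious events, and Table 2.20 is a listing. All the summaries are n (%) by arm. None gives time at risk, a rate or a stated window. SAP 9.8 adds "Safety analysis will consist of tabulating the frequency of serious adverse events" and places safety inside the primary outcome analysis.

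On follow-up, SAP 6.7.2 says "Minimum length of follow up for the pilot will be 3 months from treatment for each patient" and starts the visit clock at the end of treatment: catheter removal, or the last radiation fraction. SAP 10.4 names Visit 3 as the last feasibility visit.

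Time before that clock starts differs by design. SAP 6.2.2 puts an 84-day drug phase before focal therapy in two CHRONOS-B arms. For radiotherapy men in CHRONOS-A, SAP 6.2.1 has "neoadjuvant ADT permitted and if given, minimum 3 months and maximum 6 months duration".

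The protocol describes the window differently. The table in Protocol 2.7 counts a three-month minimum from randomisation. Protocol 8.1.1 gives six months of safety follow-up if the study stops after the pilot.

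**The concern.** The percentage of men with at least one event, and the worst grade per man, both rise with time observed even when the underlying rate is the same. If events count from randomisation to Visit 3, the drug phase or hormone phase adds observation time in some arms only. Background events in that time would then look like harm from the drug or the radical strategy. Events before ablation and after it also fall in the same cell, so the tables cannot show which phase produced a difference.

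The by-arm tables are the planned summary of pilot safety. Protocol 1.2.1 speaks of stopping arms with too high an adverse event rate, and Protocol 11.4 lists harm in an arm as a reason to discontinue. Pilot men are also carried into the main stage.

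**Working it through.** **The plan's own figure.** The Trial Summary gives 12 months' recruitment, at least 3 months' follow-up and 15 months in total: 12 + 3 = 15, as stated. For the last man recruited, this works only if the 3 months run from randomisation. Counted from treatment, with 84 days = 2.76 months, the last drug-arm man needs 12 + 2.76 + 3 = 17.76 months. The stated total therefore does not settle which window applies.

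**Inputs from the documents.** Drug phase 84 days; hormones 3 to 6 months if given; Visit 3 at 3 months (13 weeks) after treatment; 20 men per CHRONOS-B arm.

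**Assumptions (not in the documents).** Focal therapy 4 to 8 weeks after randomisation in controls and 12 to 16 weeks in drug arms; a radiotherapy course of 1 to 2 months; a constant event rate, equal in all arms; 30% or 50% of controls with an event; events counted from randomisation to Visit 3.

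**CHRONOS-B.** Observation is 4 + 13 = 17 to 8 + 13 = 21 weeks in controls, and 12 + 13 = 25 to 16 + 13 = 29 weeks in drug arms. With rate λ = −ln(1 − p_control)/T_control, the drug-arm percentage is 1 − exp(−λ × T_drug).

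| Control v drug (weeks) | Difference | Ratio | 30% becomes | 50% becomes |
|---|---|---|---|---|
| 21 v 25 | 4 | 1.19 | 34.6% | 56.2% |
| 21 v 29 | 8 | 1.38 | 38.9% | 61.6% |
| 17 v 25 | 8 | 1.47 | 40.8% | 63.9% |
| 17 v 29 | 12 | 1.71 | 45.6% | 69.3% |

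**Where the ratio is 1.0.**
- Controls wait as long as the drug phase: 2.76 + 3 = 5.76 months in both arms.
- Events are counted only from Visit 2 to Visit 3: 3 months in every arm.
- A common calendar cut-off at month 15 with uniform accrual: a mean of 15 − 6 = 9 months from randomisation in every arm.
- A fixed window from randomisation. Total time is then equal, but post-ablation time is not: in a 13-week (91-day) window, a drug-arm man has at most 91 − 84 = 7 days left after the drug phase.

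**CHRONOS-A.** Hormones plus radiotherapy give 3 + 1 + 3 = 7 to 6 + 2 + 3 = 11 months, against 4 to 5 months for focal men who wait 1 to 2 months. The ratio is 7/5 = 1.4 to 11/4 = 2.75. This is a subset, not an arm. If it makes up 10% to 50% of the radical arm and all other men are observed for 4 months, the arm-level ratio runs from (0.1 × 7 + 0.9 × 4)/4 = 1.08 to (0.5 × 11 + 0.5 × 4)/4 = 1.88.

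**Against sampling error.** With 20 per arm, the standard error of a difference is √[p₁(1 − p₁)/20 + p₂(1 − p₂)/20], which is about 15 to 16 points for every pair in the table. The artefacts are 4.6 to 15.6 points from a 30% base and 6.2 to 19.3 points from a 50% base. Six of the eight are below one standard error. The two from the 17 v 29 week pair slightly exceed it, and none reaches 1.96 standard errors (about 30 points).

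**The case against.** A reader might infer that drug-arm men are observed at least 12 weeks longer and must show more events by construction. The documents do not support that. They give no waiting time for focal therapy alone, and 12 weeks is the largest difference in the table above, not the smallest. Three months is a minimum, and the protocol gives other windows. The visit schedule first lists adverse event review at Visit 2, and counting from there would equalise the arms. These points stand, and they make the size of any imbalance unknown.

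The Visit 2 reading fits poorly with the rest of the plan, however. Table 2.17 has columns for relationship to, and action taken on, the study drug, and the drug phase comes before focal therapy. Protocol 7.2 counts important laboratory abnormalities in the two drug arms as adverse events.

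It is also fair to say that the summary is descriptive. No between-arm test is planned, and the numerical progression criteria in SAP 9.3 and SAP 11 concern compliance and recruitment, not adverse events. Tables 2.19 and 2.22 show causality, and Tables 2.4 and 2.5 report the pre-treatment intervals by arm, though nothing connects those intervals to the event tables.

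Finally, extra events during drug or hormone exposure are partly real effects of the allocated strategy. That stands too. Many expected toxicities are left out of Tables 2.18 and 2.19 through Appendix 1, so what remains leans more towards background events, but not wholly.

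**Conclusion.** The point holds in a limited form. The SAP defines no start date, end date or time at risk for pilot adverse events, and the documents disagree on the follow-up window. Crude percentages may therefore not be comparable between arms. Under the stated CHRONOS-B assumptions the observation ratio is about 1.2 to 1.7. It is 1.0 under other readings that the text does not exclude. In CHRONOS-A the larger gap belongs to an optional subset of the radical arm.

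The documents do not support saying that a bias is certain, or that a pilot decision rests on it: no progression rule uses these tables, and at 20 men per arm chance variation mostly exceeds the artefact. This is a worthwhile improvement to reporting, not a threat to the pilot's validity.

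**What to change.** - State in SAP 9.3 when adverse event observation starts and ends for the pilot, and reconcile Protocol 2.7, Protocol 8.1.1 and SAP 6.7.2 on the start and length of follow-up.
- In Tables 2.18 to 2.22, split events by onset date into (a) randomisation to the start of focal or radical treatment, including any drug or hormone phase; (b) start of treatment to Visit 2; and (c) Visit 2 to Visit 3. Period (c) is the same nominal three months in every arm. The boundary at the start of treatment keeps drug-phase events apart from peri-procedural ones.
- Show person-months by arm in each period, as a supplement only. Hazard is likely to cluster around the procedure, so a rate pooled over all periods would be diluted by a long, quiet drug phase.
- Keep the overall percentages.

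The cost is some programming and more table rows. Onset, randomisation, focal therapy and visit dates are already listed in SAP 8.3 and in the listing tables. For the radical arm, SAP 8.3 names only the treatment visit date, while SAP 10.1 relies on a treatment start date, so check that the start date is held.

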9.4. Secondary End Point Analysis

PROMs are collected throughout the feasibility phase at screening and 3 months.

EQ-5D-5L has five dimensions: mobility, self-care, usual activities, pain/discomfort, anxiety/depression, each measured using five levels of response (see Appendix 2). Summary statistics, by treatment arm, will be presented for each of the dimensions and levels, at each time point. Histograms will also be produced to display the proportions in each level for each dimension.

EQ VAS is an additional question on the EQ-5D-5L (see Appendix 2). This will be summarised, by treatment arm, at each time point.

IIEF15 consists of five domains: erectile function, orgasmic function, sexual desire, intercourse satisfaction and overall satisfaction (see Appendix 2). Summary statistics, by treatment arm, will be presented for each domain, at each time point.

EPIC-26 consists of five domains: urinary incontinence, urinary irritative/obstructive, bowel, sexual, hormonal (see Appendix 2). The response scores will be standardised using the method described in appendix 2. Summary statistics, by treatment arm, will be presented for each domain, at each time point.

EPIC-URINARY DOMAIN consists of four subscales: function, bother, incontinence and irritative/obstructive (see Appendix 2). The response scores will be standardised using the method described in appendix 2. Summary statistics, by treatment arm, will be presented for each domain, at each time point.

9.5. Impact of the Covid-19 Pandemic

To assess the impact of the Covid-19 pandemic on the feasibility phase of the trial, we will assess the baseline demographics, recruitment rate, randomisation rate, reasons for ineligibility, and time between consent and randomisation to see if there exist important differences between the population recruited before the Covid-19 pandemic and the population recruited during/after the Covid-19 pandemic.

Time between randomisation and treatment, treatment compliance (CHRONOS-A and CHRONOS-B) and drug compliance (CHRONOS-B) will be assessed between the population who

Imperial Clinical
Trials Unit

STATISTICAL ANALYSIS PLAN: FEASIBILITY

CHRONOS

underwent treatment before the Covid-19 pandemic and those who underwent treatment during/after the Covid-19 pandemic.

Time between consecutive visits will be assessed between the population who underwent their most recent consecutive visit before the Covid-19 pandemic and those who underwent their most recent consecutive visit during/after the Covid-19 pandemic. Similarly, proportions of patients with missing or delayed visits will be assessed between patients who underwent that visit before the Covid-19 pandemic and those who underwent that visit during/after the Covid-19 pandemic.

Reasons for withdrawal will be assessed between the population who withdrew before the Covid-19 pandemic and the population who withdrew during/after the Covid-19 pandemic.

Trial processes and conduct will also be assessed for important differences between these populations. This analysis is detailed further in Section Error! Reference source not found.

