11.10 Publication and Dissemination policy	60
12. REFERENCES	62
SIGNATURE PAGE 1 (Chief Investigator)	64
SIGNATURE PAGE 2 (Sponsor)	65

Short Title:	Protocol No:	Sponsor:	Version: 5.0
IP4 - CHRONOS	19CX5006	Imperial College London	Date:
			13 th July 2022

SIGNATURE PAGE 3 (Statistician)66	
SIGNATURE PAGE 4 (Principal Investigator)67	

TRIAL SUMMARY

TITLE	Comparative Health Research Outcomes of NOvel Surgery in prostate cancer			
AIM	To deliver an overarching RCT framework to efficiently evaluate novel surgical techniques in the treatment of non-metastatic prostate cancer			
	CHRONOS-A Pilot: To determine if men will agree to participate in an RCT that randomly assigns them to focal therapy alone or radical therapy (radiotherapy or prostatectomy).			
	Main: To determine if focal therapy alone is non-inferior when compared to radical therapy (radiotherapy or surgery) in terms of progression-free survival (PFS) at 5 years in men with clinically significant non-metastatic cancer.			
	CHRONOS-B Pilot: To determine if men expressing a preference for focal therapy will agree to participate in a multi-arm, multi-stage (MAMS) RCT that randomly assigns them to focal therapy alone or focal therapy in combination with neoadjuvant and/or adjuvant agents.			
	Main: To determine if focal therapy combined with neoadjuvant and/or adjuvant agents, compared to focal therapy alone, will improve failure-free survival (FFS) at 5 years, in men with clinically significant non-metastatic cancer			
PHASE	Phase II Randomised Control Trial (RCT) incorporating an internal pilot			
DURATION	Pilot: Recruitment 12 months. Minimum 3 months follow-up. Total 15 months. Main study: Recruitment further 48 months. Total including follow-up = 96 months			
DESIGN	Randomised controlled trial Two linked RCTs with CHRONOS-A and CHRONOS-B discussed with patients and choice of A or B dependent on physician and patient equipoise.			
	- CHRONOS-A Two arm RCT			
	- CHRONOS-B Multi-Arm Multi-Stage (MAMS) Randomised Control Trial			

Short Title: IP4 - CHRONOS	Protocol No: 19CX5006	Sponsor: Imperial College London	Version: 5.0 Date: 13 th July 2022
			10 daily 2022

SAMPLE SIZE	Eggeihility/nilot		
SAIVIPLE SIZE	Feasibility/pilot		
	CHRONOS-A 60 patients over 12-months (These participants will form part of the main study if feasibility is met and funding obtained)		
	CHRONOS-B 60 patients over 12-months (These participants will form part of the main study if feasibility is met and funding obtained)		

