8.3. Primary End Point Variables

Numbers of men approached for CHRONOS-A and CHRONOS-B per month per centre

- Numbers of men recruited to CHRONOS-A and CHRONOS-B per month per centre
- Numbers of men randomised to CHRONOS-A and CHRONOS-B per month per centre
- Total number of men completing each stage for each treatment arm of CHRONOS-A and CHRONOS-B
- Number of days between consent and randomisation in days:
 - o Date of consent
 - o Date of randomisation
- Number of days between randomisation and start of treatment (CHRONOS-A and CHRONOS-B):
 - Date of randomisation
 - o Date of focal therapy (CHRONOS-A (Focal arm) and CHRONOS-B)
 - Date of treatment visit (CHRONOS-A (Radical arm))
- Treatment form information and date of visit (collected at Visit 2) (CHRONOS-A and CHRONOS-B)
- Focal therapy information (collected at Visit 2) (Focal arm of CHRONOS-A and CHRONOS-B):
 - Date of Focal Therapy
 - o Form of Focal therapy performed
 - o Focal therapy ablation schema
 - Seminal vesicle treatment
- Radiotherapy/Prostatectomy information (collected at Visit 2) (Radical therapy arm of CHRONOS-A):
 - Radiotherapy/Brachytherapy Log (CHRONOS-A (Radical therapy)):
 - Form of radiation treatment undergone
 - Radiotherapy treatment details (which radiotherapy regime was performed, whether the patient had lymph node radiotherapy, whether patient completed their radiotherapy course)
 - Brachytherapy treatment details (whether the patient underwent treatment as planned, whether the patient underwent radiotherapy boost alongside brachytherapy, confirmed on post-procedure dosimetry).
 - Prostatectomy Log (CHRONOS-A (Radical therapy)):
 - Whether the patient underwent radical prostatectomy or not.
- Neoadjuvant drug information (collected at Visit 2) (CHRONOS-B):
 - Date neoadjuvant treatment was commenced
 - o Whether empty blister pack has been returned
 - Date empty blister pack was returned
 - Registered protocol deviations for drug compliance
 - Registered protocol deviations which state that the drug was taken for less than 8 weeks
- Number of days between consecutive visits:
 - Date of visit
- Number of days between randomisation and start of neoadjuvant drug treatment (CHRONOS-B):
 - Date of randomisation
 - Date neoadjuvant drug treatment commenced (CHRONOS-B)
- Number of days between start of neoadjuvant drug treatment and start of focal therapy (CHRONOS-B)
- Occurrence of adverse events not listed in Appendix 1 (see Section).

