10.1. Analysis Populations

On 05/03/2020, Covid-19 was added to Public Health England's list of notifiable diseases in England and Wales (11).

Analysis Population	Population Definition	End Points
Patients randomised	Patients randomised to the trial	Baseline demographics
before the Covid-19 pandemic	before 05/03/2020	 Recruitment rate Reasons for ineligibility
 Patients randomised during/after the Covid-19 pandemic 	Patients randomised to the trial on/after 05/03/2020	Time between consent and randomisation
 Patients who underwent radical or focal treatment before the Covid-19 pandemic 	Patients whose radical or focal treatment start date is before 05/03/2020	 Time between randomisation and treatment Treatment compliance
Patients who underwent radical or focal treatment during/after the Covid-19 pandemic	Patients whose radical or focal treatment start date is on/after 05/03/2020	(CHRONOS-A and CHRONOS-B)
Patients who started neoadjuvant drug treatment before the Covid- 19 pandemic	 Patients whose neoadjuvant drug treatment start date is before 05/03/2020 (CHRONO- B only) 	Drug compliance (CHRONOS-B)
 Patients who started neoadjuvant drug treatment during/after the Covid-19 pandemic 	Patients whose neoadjuvant drug treatment start date is on/after 05/03/2020 (CHRONOS-B only)	
Patients who underwent their most recent consecutive visits before the Covid-19 pandemic	 Patients whose most recent date of visit is before 05/03/2020 	Time between consecutive visits
 Patients who underwent their most recent consecutive visits during/after the Covid-19 pandemic 	Patients whose most recent date of visit is on/after 05/03/2020	
 Patients who attended the visit in question before Covid-19 pandemic 	Patients whose date of visit is before 05/03/2020	 Proportions of patients with missing or delayed visits
 Patients who attended the visit in question after the Covid-19 pandemic 	Patients whose date of visit is on/after 05/03/2020	
 Patients who withdrew from the trial before the Covid- 19 pandemic 	Patients whose withdrawal date if before 05/03/2020	Reasons for withdrawal
 Patients who withdrew during/after the Covid-19 pandemic 	Patients whose withdrawal date is on/after 05/03/2020	

The following analyses will only be presented is there exist patients in both the before and during/after Covid-19 pandemic populations. Analyses for populations which do not contain any patients will be omitted as they are already included in the main analysis outlined in Section 9.

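### The Covid-19 comparison of time from randomisation to treatment is split by treatment date, which truncates the 'before' waits and builds in a longer 'during/after' wait even with no pandemic effect

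*SAP*

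**What the plan says.** The end point, in SAP 8.3, is "Number of days between randomisation and start of treatment (CHRONOS-A and CHRONOS-B"). For the pandemic comparison, SAP 9.5 states: "Time between randomisation and treatment, treatment compliance (CHRONOS-A and CHRONOS-B) and drug compliance (CHRONOS-B) will be assessed between the population who" "underwent treatment before the Covid-19 pandemic and those who underwent treatment during/after the Covid-19 pandemic". The population table in SAP 10.1 fixes the two groups as "Patients whose radical or focal treatment start date is before 05/03/2020" and "Patients whose radical or focal treatment start date is on/after 05/03/2020". SAP 10.3 uses the same populations. So do Tables 6.11 and 6.12 (CHRONOS-A) and Tables 6.15 and 6.16 (CHRONOS-B); the CHRONOS-B tables also cover randomisation to drug start and drug start to focal therapy.

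Other end points are handled differently. Recruitment rate and time from consent to randomisation are split by randomisation date (for the later group, "Patients randomised to the trial on/after 05/03/2020"). Time between consecutive visits is split by the later visit of the pair ("Patients whose most recent date of visit is before 05/03/2020" for the earlier group).

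The planned output is N, mean, SD, median, IQR and number missing, by arm, with no test. SAP 10.1 drops the comparison if either group is empty. The SAP gives no alternative split of time to treatment, no censoring at the cut date and no caution about truncation.

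**The concern.** The date that decides a man's group is the date on which his measured interval ends, so group membership depends on the outcome. Take two men randomised on 1 February 2020. One is treated on 20 February, after 19 days, and is 'before'. The other is treated on 10 March, after 38 days, and is 'during/after', although 33 of his 38 days fell before 5 March. For men randomised on 1 February, no wait of 33 days or more can appear in the 'before' group.

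SAP 9.5 exists to show whether the pandemic made an important difference to the pilot. With this rule a longer later wait is expected whether or not the pandemic changed anything. The pilot report could describe a treatment delay that did not happen, or overstate one that did, and main-stage timelines could be planned around it.

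**Working it through.** **Algebra.** Let R be the randomisation date, W the wait and C = 05/03/2020. The SAP's 'before' group is R + W < C, that is, W < C - R. This is right truncation. Men with R < C and W ≥ C - R go to 'during/after' with the whole of W. If W varies between men and does not depend on calendar time, the mean of W is pulled down in 'before' and up in 'during/after'. If every man waits equally long, the difference is zero. The direction needs no further assumption; the size does.

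**Inputs from the documents.** Cut date 05/03/2020 (SAP 10.1). Twelve months' pilot accrual (Protocol Trial Summary: "Pilot: Recruitment 12 months. Minimum 3 months follow-up. Total 15 months"). Planned arms of 30 in CHRONOS-A and 20 in CHRONOS-B (SAP 6.2.3). Planned drug period of 84 days (SAP 6.2.2). The SAP gives no figure of its own for this comparison, so there is none to reproduce.

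**Assumptions, because the documents do not give them.** Uniform accrual; recruitment opening 3, 4 or 6 months before the cut; lognormal waits, with median 42 days and log-SD 0.5 (focal) or median 90 and log-SD 0.6 (radical). The true means are 42 × exp(0.5²/2) = 47.6 and 90 × exp(0.6²/2) = 107.8 days.

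**Result with no pandemic effect, grouped by treatment date (Monte Carlo).**

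| Opening before cut | Focal: before v after (difference), days | Radical: before v after (difference), days |
|---|---|---|
| 3 months | 36.5 v 49.2 (12.7) | 48.6 v 110.3 (61.7) |
| 4 months | 39.7 v 49.6 (9.9) | 58.0 v 112.9 (54.9) |
| 6 months | 42.9 v 50.4 (7.5) | 71.4 v 118.5 (47.1) |

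**Other wait shapes.** With gamma waits (mean 60 days, shape 2), the false delay is 30.6, 26.0, 20.7 and 20.2 days for opening 3, 4, 6 and 9 months before the cut. It is 10.1 days for opening 12 months before with 24 months' accrual. Over mean waits of 30 to 90 days and the opening dates tried, it runs from 2.5 to 65.5 days.

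**Chance in one pilot.** With the focal wait and an arm of 30 or 20 men, the 'after' mean is the larger in about 76-91% of pilots, against roughly half if the grouping were neutral.

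**Drug arms.** With 84 days of the wait planned, few men can be 'before'. In the gamma settings (84 days plus a mean of 30 or 60) the share is 0-0.1% for opening 3 months before the cut and 1.5-3.6% for 4 months. The false delay is 16-44 days at 4 months and 8-29 days at 6 months. With a tighter remainder (lognormal, median 21, log-SD 0.5) it is 108.1 - 101.0 = 7.1 and 108.3 - 105.7 = 2.6 days.

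**Two simpler repairs, tested.**
- *Group by randomisation date only.* With no effect the bias disappears. But with opening 3 months before the cut, about half of focal men and 82% of radical men randomised before it are still waiting on that date. Adding an assumed 60-day pause in treatment from 5 March gives 78.0 v 54.2 days (focal) and 157.0 v 114.3 days (radical). The pause would appear to have shortened waits.
- *Treatments per waiting day, before and after the cut.* With no effect this gives 0.0154 v 0.0221 per day for the focal arm (3 months), an apparent speeding-up. The chance of treatment changes with time since randomisation, and a crude rate ignores that.

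**The case against.** The strongest reply is that little hangs on this comparison. It is descriptive and has no threshold. The numerical progression criteria in SAP 9.3 and 11 concern compliance and recruitment, the undivided waiting times are still reported in Tables 2.4 and 2.5, and the comparison is dropped if one group is empty. All of this stands and limits the consequence, but it does not make the split informative.

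The size also rests on assumed opening dates and waits. That stands too: the bias shrinks as the pre-pandemic period lengthens, though its direction does not change.

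A reader might infer more than the documents support:
- *That 'before' can hold only short waits.* The limit is the time from each man's randomisation to the cut. With opening 6 months earlier, the focal 'before' mean is 42.9 days against a true 47.6.
- *That the bias is largest in the drug arms because their waits are longest.* Truncation acts on the spread of waits, and 84 days are planned. The main problem there is a nearly empty 'before' group.
- *That visit intervals are distorted to the same extent.* The mechanism is the same, but the size was not quantified. Visit 2 to Visit 3 is scheduled at 3 months with a window of 4 weeks either way, which limits its planned spread.

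**Conclusion.** The rule is wrong as written for the question that SAP 9.5 asks. Splitting time to treatment by treatment date right-truncates the 'before' waits and produces an apparent pandemic delay whenever waits vary. Under the stated assumptions, the false difference in means is about 7 to 13 days in the focal arm and 47 to 62 days in the radical arm. Other plausible settings give anything from a few days to about two months. In the drug arms the chief consequence is that hardly anyone can be in the 'before' group.

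A reader might infer that progression to the main stage is at risk. The documents do not support that, because waiting time is not one of the numerical progression criteria. The harm is a misleading statement about the pandemic in the pilot report. The change is worth making because it costs little.

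**What to change.** In SAP 9.5, 10.1, 10.3 and Tables 6.11, 6.12, 6.15 and 6.16, replace the treatment-date split with a Kaplan-Meier summary of time to treatment, by arm, on time since randomisation:

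- **Before:** men randomised before 05/03/2020, with those still waiting on that date censored there.
- **During/after:** men randomised on or after 05/03/2020, plus men still waiting on that date, who enter late at their elapsed wait.

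Apply the same method to randomisation to drug start, to drug start to focal therapy (from drug start), and to consecutive visits (from the earlier visit of the pair). Do not rely on randomisation-date grouping alone, which can reverse the sign of a true delay, or on a crude rate per waiting day, which is biased with no effect.

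**Cost.** SAP wording, table shells and slightly more analysis; the dates are already collected (SAP 8.3). Estimates will be imprecise where few men are at risk, and the 'before' curve cannot extend past the time from opening to 05/03/2020. The periods should be compared only over the range that both cover, with numbers at risk shown.
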